9.2.2.2 Reporting a Safety Endpoint as a Study Endpoint

The investigator is responsible for ensuring that all serious adverse events/adverse events observed by the investigator or reported by the subject that occur after signing of the informed consent or randomization, respectively, through the Safety Follow-up Visit/EOS are reported using the applicable eCRF (eg, Event eCRF), including events that are reported to the CEC committee for adjudication.

9.3 Pregnancy and Lactation Reporting

If a pregnancy occurs in a female subject, or female partner of a male subject, while the subject is taking protocol-required therapies report the pregnancy to Amgen as specified below.

In addition to reporting any pregnancies occurring during the study, investigators should report pregnancies that occur after the last dose of protocol-required therapies through 5 days following the last dose of IP.

The pregnancy should be reported to Amgen Global Patient Safety within 24 hours of the investigator's knowledge of the event of a pregnancy. Report a pregnancy on the Pregnancy Notification Worksheet ([Appendix C](#)).

If a lactation case occurs while the female subject is taking protocol-required therapies report the lactation case to Amgen as specified below.

In addition to reporting a lactation case during the study, investigators should report lactation cases that occur after the last dose of protocol-required therapies through 5 days following the last dose of IP.

Any lactation case should be reported to Amgen Global Patient Safety within 24 hours of the investigator's knowledge of event. Report a lactation case on the Lactation Notification Worksheet ([Appendix C](#)).

10. STATISTICAL CONSIDERATIONS

10.1 Study Endpoints, Analysis Sets, and Covariates

10.1.1 Study Endpoints

10.1.1.1 Primary Endpoints

- Concentrations prior to administration (Cpredose) of omecamtiv mecarbil at weeks 2, 4, 12, and 16, and area under the curve (AUC) at week 8

10.1.1.2 Secondary Endpoint

- Changes from baseline in SET by echocardiography at week 16

10.1.1.3 Safety Endpoints

- Subject incidence of adverse events
- Changes from baseline in laboratory values and vital signs
- Changes from baseline in ECG

10.1.1.4 Exploratory Endpoints

Exploratory endpoints are as follows:

- observed values and change from baseline to assessed timepoints of stroke volume, left ventricular end-systolic diameter (LVESD) and left ventricular end-dyastolic diameter (LVEDD).
- observed values and change from baseline to assessed timepoints of HR
- observed values and change from baseline to assessed timepoints of NT-proBNP
- subject incidence of supraventricular tachycardia and ventricular tachycardia arrhythmias requiring treatment from initiation of IP to EOS
- subject incidence of the following clinical outcome endpoints:
 - cardiovascular death or HF hospitalization until EOS
 - all-cause death or HF hospitalization until EOS
 - all adjudicated events until EOS; events include, but may not be limited to: cardiovascular death, HF, acute myocardial infarction, myocardial ischemia, unstable angina, and resuscitated sudden death
 - new onset atrial fibrillation/flutter
 - all-cause death

10.1.2 Analysis Sets

The PK analysis set (PKAS) includes all randomized subjects who have received at least one dose of omecamtiv mecarbil and have at least one evaluable omecamtiv mecarbil PK parameter (C_{max} , $C_{predose}$). This analysis set will be used for analyses of all the PK endpoints, unless significant protocol deviations have affected the data or if key dosing or sampling information are missing, in which case a modified PKAS will be used.

The full analysis set (FAS) includes all randomized subjects who have received at least one dose of IP (omecamtiv mecarbil or placebo). This set will be used for all analyses of non-PK endpoints.

The completers analysis set is a subset of the FAS and includes subjects who have completed IP administration. The completers analysis set will be used for sensitivity analyses.

Approved

10.1.3 Covariates and Subgroups

The stratification factor is presence or absence of atrial fibrillation/flutter. Other baseline covariates include the following:

- age (< 65, ≥ 65)
- sex
- LVEF
- Body mass Index (BMI)
- NT-proBNP
- presence of coronary artery disease
- HF treatment at baseline

10.2 Sample Size Considerations

The primary endpoints of this study are the omecamtiv mecarbil PK parameters. PK parameter's mean will be estimated. Assuming the SDs for C_{max} and AUC are in the range of 40 to 90, a sample size of n= 20 subjects in each treatment group, 19 subjects (assuming 5% subjects out of a total n = 20 subjects per treatment arm are excluded from PKAS) will provide a 2-sided 95% confidence interval (CI) with half width of 18 to 41. The SD estimates are from the predicted steady state PK for 25 mg and 50 mg BID doses for Matrix F1 formulation based on simulations performed using PK data following single dose from study 20090727. [Table 4](#) below presents CI half widths given particular SDs in this range for 19 subjects per treatment group.

Table 4. PK Parameter 95% Confidence Intervals

Standard Deviation	Confidence Interval Half Width	
	N=19	
40		18.0
50		22.5
60		27.0
70		31.5
80		36.0
90		40.5

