Prior to initiation of subject enrollment into this study (Study 20120227) results from the planned Japanese phase 1 study 20150134, which include PK and safety assessments of repeated 25 mg BID, 37.5 mg BID, and 50 mg BID oral dosing, will be reviewed. It is expected that Study 20150134 will confirm the doses selected are appropriate to be studied in this phase 2 study (Study 20120227).

Study 20120227 will enroll approximately 80 subjects and randomize them to doses of omecamtiv mecarbil (25 mg, 37.5 mg, or 50 mg BID), or placebo. Simulated omecamtiv mecarbil exposures in subjects with low body weight, defined as less than 58 kg based on the median body weight distribution of Japanese subjects with HF, were approximately 25% to 35% higher compared with exposures in non-Japanese HF subjects with a higher body weight, defined as greater than 82 kg based the median body weight of subjects with HF in the ATOMIC-AHF and COSMIC-HF studies (Table 1).

Table 1. Comparison of Omecamtiv Mecarbil Steady State C_{max} and AUC Following BID Dosing of MR-F1 Tablets in Healthy Japanese Subjects

BID Dose (mg)	Simulated Japanese		Simulated Non-Japanese	
	$C_{max,ss}$ (ng/mL)	AUC _{ss} (ng*hr/mL)	$C_{max,ss}$ (ng/mL)	AUC _{ss} (ng*hr/mL)
25	277 [252] (129)	2759 [2501] (1305)	211 [193] (94)	2115 [1918] (962)
37.5	461 [418] (214)	4613 [4171] (2185)	351 [319] (155)	3521 [3201] (1585)
50	614 [557] (286)	6143 [5539] (2929)	469 [427] (209)	4707 [4265] (2130)

Data presented as mean [median] (standard deviation); AUC_{ss} = area under the curve, steady state; C_{max} = maximum plasma concentration; HF = heart failure; BID = twice daily

Though the results of the completed phase 1 Study 20120255 showed that systemic clearance in Japanese and Caucasian subjects was not statistically significantly different, and that the body weight adjusted clearance was essentially identical, this study will include an additional tablet strength of 37.5 mg BID to further explore PK and PD parameters with chronic repeated oral dosing.

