2.4 Clinical Hypotheses

No formal hypothesis testing will be performed. PK parameters following chronic dosing (BID for 16 weeks) will be estimated.

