50 mg BID at the week 4 visit based on steady state concentration prior to investigational product (IP) administration ($C_{predose}$) result from week 2. Subjects who do not have a week 2 PK value in time for dose adjustment at the week 4 visit will be up-titrated at week 8 based on the steady state $C_{predose}$ result from week 2, if available. Subjects will be up-titrated at the week 4 or week 8 visits only if the week 2 $C_{predose}$ is < 200 ng/mL. Subjects with a week 2 $C_{predose} \geq 200$ ng/mL (or not available at week 8) will continue at 25 mg BID for the remaining of the study. Subjects randomized to placebo or to 25 mg BID will receive the assigned IP throughout the study. IP compliance will also be monitored. PK analysis and dose assignment will be blinded to the study team. To maintain blinding, all subjects will receive new IP supply at the week 4 and week 8 visits. The study includes transthoracic echocardiographic assessments (screening, week 8, and week 16). Enrollment of subjects with atrial fibrillation/flutter at the time of screening will be limited to approximately 20% of planned enrollment. Randomization will be stratified by presence or absence of atrial fibrillation/flutter via the interactive voice response system/interactive Web response system (IVRS/IWRS). An independent DMC will perform regular formal unblinded review of the accumulating study data. An independent CEC will adjudicate deaths, all hospitalizations, and selected nonfatal cardiovascular (CV) events (including possible MI or ischemia). The end of study (EOS) visit will be performed 4 weeks after the last dose of IP (Week 20 +3 days).

Vital signs, physical examinations, ECGs, Adverse Event/Serious Adverse Event assessments, clinical laboratory evaluations (see [Table 3](#)), and collection of concomitant medications will be performed at screening and at specified times per the Schedule of Assessments ([Table 2](#)). The overall study design is described in a [study schema](#) at the end of the protocol synopsis section.

The study endpoints are defined in [Section 10.1.1](#).

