5.1 Randomization/Treatment Assignment

Subjects will be randomized in a 1:1:1:1 manner to receive either 25 mg BID omecamtiv mecarbil dose (n=20), 37.5 mg BID omecamtiv mecarbil dose (n=20), 50 mg BID omecamtiv mecarbil dose (n=20) or placebo (n=20) on an outpatient basis. Subjects randomized to 37.5 mg BID target dose and 50 mg BID target dose will initiate administration at 25 mg BID and will be up-titrated to the 37.5 mg BID or 50 mg BID target dose at the week 4 visit based on steady state $C_{predose}$ result from week 2.

Approved

Subjects who do not have a week 2 PK value in time for dose adjustment at the week 4 visit will be up-titrated at week 8 based on steady state $C_{predose}$ result from week 2, if available. Subjects will be up-titrated at the week 4 or week 8 visit only if the week 2 $C_{predose}$ is < 200 ng/mL. Subjects with a week 2 $C_{predose} \geq 200$ ng/mL (or not available at week 8) will continue at 25 mg BID for the remainder of the study. Subjects randomized to placebo or to 25 mg BID will receive the assigned IP throughout the study. To maintain blinding, all subjects will receive new IP supply at week 4 and week 8 visits. There is no other dose adjustment for individual subjects during the study.

Assignment to the treatment arms will be based on a computer-generated randomization schedule prepared by Amgen before the start of the study. A subject may only receive one randomization number and each randomization number will only be assigned to 1 subject.

Once eligibility into the study has been confirmed, a site representative will make the randomization call to the IVRS/IWRS to assign a randomization number to the subject. The randomization call to the IVRS/IWRS is accomplished by entering the pertinent information detailed in the IVRS/IWRS user manual. A confirmation will be sent to the site to verify that the correct information has been entered and to confirm the randomization assigned. A subject will be considered enrolled and randomized into the study when a randomization number is assigned.

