3.2 Sample Size

The primary endpoints of this study are the omecamtiv mecarbil PK parameters. PK parameter's mean will be estimated. Assuming the SDs for C_{max} and AUC are in the range of 40 to 90, a sample size of $n= 20$ subjects in each treatment group, 19 subjects (assuming 5% subjects out of a total $n = 20$ subjects per treatment arm are excluded from PKAS) will provide a 2-sided 95% confidence interval (CI) with half width of 18 to 41. The SD estimates are from the predicted steady state PK for 25 mg and 50 mg BID doses for Matrix F1 formulation based on simulations performed using PK data following single dose from study 20090727. The table below presents CI half widths given particular SDs in this range for 19 subjects per treatment group.

PK Parameter 95% Confidence Intervals

Standard Deviation	Confidence Interval Half Width	
	N = 19	
40		18.0
50		22.5
60		27.0
70		31.5
80		36.0
90		40.5

4. Study Endpoints and Covariates

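### The Table 4 precision statement ignores the titration rule, so it does not describe the 37.5 mg and 50 mg arms under either way of grouping the PK data

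*Protocol*

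**What the plan says.** The study is sized on precision alone; Protocol 2.4 says "No formal hypothesis testing will be performed. PK parameters following chronic dosing (BID for 16 weeks) will be estimated". Protocol 10.2 starts from "Assuming the SDs for C_{max} and AUC are in the range of 40 to 90" and from "19 subjects (assuming 5% subjects out of a total n = 20 subjects per treatment arm are excluded from PKAS"). It concludes, in words that SAP 3.2 repeats, that this n "will provide a 2-sided 95% confidence interval (CI) with half width of 18 to 41". On the source of the SDs it says "The SD estimates are from the predicted steady state PK for 25 mg and 50 mg BID doses for Matrix F1 formulation", based on simulation from single-dose data.

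Protocol 3.1 and 5.1 set the dosing. Subjects in the 37.5 mg and 50 mg arms start on 25 mg BID and move up at week 4, or at week 8 if the result is late, only if week 2 Cpredose is below 200 ng/mL. Those at or above 200 ng/mL, or with no result by week 8, "will continue at 25 mg BID for the remaining of the study". Neither sample-size section mentions this.

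The analysis text points two ways. Protocol 10.5.1 analyses subjects by randomized group. SAP 10.5 summarises each PK parameter by dose level and uses the doses actually given in the noncompartmental analysis. SAP 6.4 defines groups by titration status, for optional use in selected outputs.

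**The concern.** The one loss allowed for, 5% exclusion from the PK analysis set (PKAS), does not cover non-titration. Under SAP 7.1 a subject enters that set with one evaluable concentration, so someone who never leaves 25 mg still counts among the 19.

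Timing narrows the target-dose data further. The week 2 and week 4 predose samples precede any up-titration, so among the primary endpoints only the week 8 AUC and the week 12 and 16 Cpredose can reflect 37.5 mg or 50 mg. A subject titrated at week 8 has the AUC taken at that visit, at best on the first target dose and not at target-dose steady state.

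PK is a primary objective and these are the primary endpoints. For two of the three dose levels, a reader of Table 4 would expect 19 subjects with the spread of an unselected group at one dose. The design does not supply that.

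**Working it through.** **1. The plan's own figures.** Half-width = 1.96 × SD / √19. For SD 40, 50, 60, 70, 80 and 90 this gives 17.99, 22.48, 26.98, 31.48, 35.97 and 40.47. Every Table 4 entry is reproduced, and 20 × 0.95 = 19. The arithmetic is sound; the question is what it applies to.

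**2. Share not titrated.** No Cpredose is predicted anywhere, so a trough must be assumed. Inputs are the 25 mg BID rows of Protocol Table 1, as mean [median] (SD):

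- Simulated Japanese, described in Protocol 2.3 as below 58 kg: Cmax 277 [252] (129), AUC "2759 [2501] (1305").
- Simulated non-Japanese, above 82 kg: Cmax 211 [193] (94), AUC 2115 [1918] (962).

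Take trough as lognormal with median m = r × median Cmax and the CV of Cmax (129/277 = 0.466; 94/211 = 0.445). Then σ = √ln(1 + CV²) = 0.443 and 0.425, and P(trough ≥ 200) = 1 − Φ(ln(200/m)/σ).

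| Assumed trough/peak ratio r | Japanese | Non-Japanese |
|---|---|---|
| 0.40 | 6% | 1% |
| 0.50 | 15% | 4% |
| 0.65 | 33% | 14% |
| 0.75 | 45% | 22% |
| Ceiling: average concentration ≥ 200 | 54% | 30% |

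The last row uses median AUC/12 (2501/12 = 208; 1918/12 = 160) with the CV of AUC, assuming that AUCss covers 12 h. It is a ceiling because a trough cannot exceed the interval average. The trial enrols only Japanese subjects, so I take roughly 5% to 55% as the range. That leaves 19 × 0.95 = 18.05 down to 19 × 0.45 = 8.55, about 18 to 9 subjects on target dose. Missing week 2 results would lower this further.

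**3. Effect on precision with SD held fixed.** At n = 16, SDs of 40 to 90 give half-widths of 19.6 to 44.1; at n = 13, 21.7 to 48.9. The factors are √(19/16) = 1.09 and √(19/13) = 1.21.

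**4. Effect when selection is included.** Use the Japanese model above and assume that each subject's target-dose trough is k times the week 2 trough, with k from Table 1 mean Cmax (461/277 = 1.664; 614/277 = 2.217). With z = ln(200/m)/σ, titrated subjects have mean k·m·exp(σ²/2)·Φ(z−σ)/Φ(z) and second moment k²·m²·exp(2σ²)·Φ(z−2σ)/Φ(z). The whole arm is the mixture of these with the untitrated subjects at 25 mg. Expected titrated n is 19 × (1 − 0.149) = 16.2 at r = 0.50 and 19 × (1 − 0.326) = 12.8 at r = 0.65. Cpredose cells show mean / SD / 95% half-width in ng/mL.

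| Arm, r | 19 unselected, all at target | Titrated only | Whole arm, n = 19, mixed doses |
|---|---|---|---|
| 37.5 mg, 0.50 | 231 / 108 / 48 | 197 / 64 / 31 | 206 / 67 / 30 |
| 50 mg, 0.50 | 308 / 143 / 64 | 263 / 86 / 42 | 262 / 82 / 37 |
| 37.5 mg, 0.65 | 301 / 140 / 63 | 224 / 61 / 34 | 241 / 70 / 32 |
| 50 mg, 0.65 | 401 / 187 / 84 | 299 / 82 / 45 | 291 / 80 / 36 |

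Truncation at 200 ng/mL cuts the SD by more than the smaller n widens the interval, and it pulls the mean down. The perfect carry-over from week 2 to later troughs is the favourable extreme. As within-subject correlation weakens, the SD reduction fades and the result moves back towards step 3.

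**The case against.** Table 4 speaks of 19 subjects per treatment group, not of 19 at target dose. Under the protocol's grouping, and with PKAS membership independent of titration, that n is delivered. The term dose level in SAP 10.5 may also mean no more than the randomized arm. No hypothesis is tested and no precision target is set, so no decision is missed. The SAP already has titration-status groups. In step 4 the whole-arm half-widths of 30 to 37 even fall inside Table 4's range.

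Much of this stands. The point is a planning statement that does not match the design; it is not an arithmetic error. What does not stand is that n = 19 settles it. The SDs paired with that n are for steady state at a single dose, whereas a randomized upper arm is a mixture. The whole-arm widths land in range only because truncation happens to bring the spread there; the same model gives unselected target-dose SDs of 108 to 187. Table 4 is also framed on Cmax and AUC, so the match on Cpredose is not evidence that it was built for this case.

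A reader might infer that intervals at target dose will be 9% to 21% wider than stated. That holds only with SD fixed, and step 4 shows selection can more than offset it. A reader might also infer that the documents predict 15% to 33% non-titration. They predict no trough, and those figures are one slice of the range in step 2. Nor is every dose group affected: the 25 mg arm loses nobody to this rule.

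**Conclusion.** The concern holds in limited form. For the 37.5 mg and 50 mg arms, Protocol 10.2 and SAP 3.2 pair an n and a set of SDs that do not occur together. By dose received, n at weeks 8, 12 and 16 falls below 19 as soon as anyone is not titrated, and the mean describes a low-exposure subset (at 50 mg in the model, 263 against 308, or 299 against 401 ng/mL). By randomized arm, n is 19 and the mean blends 25 mg with the target dose.

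The size is uncertain. About 9 to 18 of 19 on target dose rests on lognormal troughs, an assumed trough/peak ratio, a CV borrowed from Cmax or AUC, and, for the upper end, AUCss per 12 h. The direction of the change in interval width is not determined by the documents, so no fixed loss of precision should be claimed.

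A separate matter bears on the rerun. Table 1 SDs (Cmax 129 to 286, AUC 1305 to 2929) lie far above the 40 to 90 used for sizing. At n = 19 they give half-widths of 58 to 129 and 587 to 1317, a larger discrepancy than titration produces.

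**What to change.** - In Protocol 10.2 and SAP 3.2, state which grouping Table 4 refers to, and reconcile Protocol 10.5.1 (randomized group) with SAP 10.5 (dose level).
- Rerun the sizing simulation with the existing week 2 rule applied, including subjects with no result and those titrated only at week 8.
- Replace the upper-arm entries with expected n, SD and half-width at weeks 8, 12 and 16 for titrated subjects, non-titrated subjects and the whole arm, over a stated range of non-titration.
- Keep n = 19 for the 25 mg arm and for whole-arm summaries, and say that the latter describe the titration strategy, not a single dose.
- Note beside any titrated-only summary that it covers subjects selected for low week 2 exposure.

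The cost is one simulation rerun and a replaced paragraph and table in two documents. The stated n at target dose becomes smaller. Enrolment and the titration rule do not change.

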4.2 Planned Covariates

Covariates include, but are not limited to the following:

Stratification Factor

- atrial fibrillation/flutter per the interactive voice response system (IVRS stratification factor) (presence vs. absence)

Baseline Covariates

- age at study enrollment (< 65 vs. ≥ 65 years)
- sex (male vs. female)
- LVEF (< median vs. ≥ median)
- body mass index (BMI) (< median vs. ≥ median)
- NT-proBNP (< median vs. ≥ median)
- coronary artery disease (CAD) (presence vs. absence)

5. Hypotheses and/or Estimations

No formal hypothesis testing will be performed and all statistical approaches are hypothesis-generating. PK parameters following chronic dosing (BID for 16 weeks) will be estimated and presented along with confidence interval limits.

6. Definitions

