10.1 General Principles

The final analysis will be conducted when all subjects have either completed all the scheduled study visits or have early terminated from the study. At that time, the database will be cleaned, processed and a snapshot will be taken; the study will also be unblinded. All endpoints will be analyzed based on this snapshot.

No formal hypothesis will be tested, and all statistical approaches are hypothesis-generating. Descriptive statistics will be presented for all endpoints.

Subject disposition, demographics, baseline characteristics and exposure to IP will be summarized.

Summary statistics for continuous variables will include number of subjects, mean, median, SD, or standard error, lower and upper quartiles, minimum, and maximum. For PK parameters, coefficient of variation (CV) will also be included. For categorical variables, frequency and percentage will be presented. Unless specified otherwise, all confidence intervals for estimates will be 2-sided with a significance level of 0.05.

Subjects will be analyzed based on their randomized or received treatment group assignment as described in [Section 7](#).

Missing data handling is specified in [Section 9.3](#).

For the secondary endpoint SET, sensitivity analyses using the CAS will be conducted to explore the robustness of selected results.

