10.5 Analyses of Primary Endpoints

The primary endpoints are omecamtiv mecarbil PK parameters $C_{predose}$ and AUC, collected in the study ([Section 4.1.1](#)).

All data for PK analyses will be extracted from a secure folder and mapped via a clinical connector into the Pharsight Knowledgebase Server (PKS) system (Pharsight Corporation, St. Louis, MO).

Omecamtiv mecarbil plasma concentration-time data will be analyzed by noncompartmental methods using Phoenix WinNonlin (Pharsight Corporation, St. Louis, MO) and will be stored in the validated PKS system. Concentration values less than or

equal to the lower limit of quantification (LLOQ, 1 ng/mL) will be set to zero in the analysis dataset. In the PK data analysis, LLOQ value (zero) will be excluded.

Actual doses administered and actual or nominal sampling times post drug administration will be used in the noncompartmental analysis. Nominal times will be used for presenting data in graphs and tables. All pharmacokinetic parameters and summary statistics will be presented to 3 significant digits.

Summary statistics of PK parameters will include mean, standard deviation and CV%; median and range; geometric mean and CV% of geometric mean. Each pharmacokinetic parameter will be summarized by dose level and sampling time.

In the pharmacokinetic analysis, the following parameters will be estimated:

- Observed maximum concentration (C_{\max})
- Observed time to achieve C_{\max} (t_{\max})
- Observed concentration prior to next dose (C_{predose})
- Area under the plasma concentration-time curve (AUC_t) calculated by linear trapezoidal method
- Ratio of $C_{\max} / C_{\text{predose}}$

Individual concentration-time data will be tabulated and presented graphically. Mean concentration-time profiles for each dose will be provided.

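### The planned 95% CI half-widths use the normal quantile 1.96 with 19 subjects and an SD to be estimated; with t on 18 df the range is 19 to 43, not 18 to 41

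*Protocol*

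**What the plan says.** Protocol 10.2 sets out an estimation design: "PK parameter's mean will be estimated". It takes as inputs an SD range, "Assuming the SDs for C_{max} and AUC are in the range of 40 to 90", with no units, and an evaluable number per arm, "19 subjects (assuming 5% subjects out of a total n = 20 subjects per treatment arm are excluded from PKAS". From these it concludes that the design "will provide a 2-sided 95% confidence interval (CI) with half width of 18 to 41". Table 4 lists the half-widths for SDs of 40, 50, 60, 70, 80 and 90 as 18.0, 22.5, 27.0, 31.5, 36.0 and 40.5. SAP 3.2 repeats the text and the table.

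Neither document gives the formula or the quantile. On where the SDs come from, the Protocol says: "The SD estimates are from the predicted steady state PK for 25 mg and 50 mg BID doses for Matrix F1 formulation". They are therefore predictions from simulation.

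For the analysis, SAP Section 5 commits to an interval: "PK parameters following chronic dosing (BID for 16 weeks) will be estimated and presented along with confidence interval limits". SAP 10.1 sets the level: "all confidence intervals for estimates will be 2-sided with a significance level of 0.05". SAP 10.5 shows that the SD will be computed from the trial's own data: "Summary statistics of PK parameters will include mean, standard deviation and CV". The SAP does not say whether the PK limits will use a normal or a t quantile.

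**The concern.** The multiplier 1.96 gives 95% coverage for a mean when the SD is known. When the SD is estimated from 19 subjects, the multiplier is the t quantile on 18 degrees of freedom, which is appreciably larger. A table built on 1.96 therefore promises tighter intervals than a valid 95% analysis will give at the same SD. This is so whatever the units or size of the SD.

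The trial tests no hypothesis, so there is no power calculation behind the sample size, and this half-width is its whole quantitative justification. Two outcomes are possible:

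- If the analysis uses t, the reported intervals will on average be wider than the plan says.
- If the analysis uses 1.96 so as to agree with the plan, the intervals will cover less than the stated 95%.

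**Working it through.** **Inputs**

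- Confidence level: two-sided 95% (Protocol 10.2; SAP 10.1).
- Evaluable subjects per arm: 20 less 5% = 19 (Protocol 10.2).
- SD: 40, 50, 60, 70, 80, 90 (Table 4).
- √19 = 4.3589; z(0.975) = 1.960; t(0.975, 18) = 2.1009.

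**Step 1: reproduce the plan's figures.** Half-width = 1.96 × SD/√19. For SD 40 this is 1.96 × 40/4.3589 = 17.99. For SD 90 it is 1.96 × 90/4.3589 = 40.47.

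**Step 2: use the t quantile.** Half-width = 2.1009 × SD/√19. For SD 40 this is 2.1009 × 40/4.3589 = 19.28. For SD 90 it is 2.1009 × 90/4.3589 = 43.38.

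| SD | Table 4 | 1.96 × SD/√19 | t(18 df) × SD/√19 | t minus z |
|---|---|---|---|---|
| 40 | 18.0 | 17.99 | 19.28 | 1.29 |
| 50 | 22.5 | 22.48 | 24.10 | 1.62 |
| 60 | 27.0 | 26.98 | 28.92 | 1.94 |
| 70 | 31.5 | 31.48 | 33.74 | 2.26 |
| 80 | 36.0 | 35.97 | 38.56 | 2.59 |
| 90 | 40.5 | 40.47 | 43.38 | 2.91 |

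The normal formula matches all six printed values to one decimal.

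**Step 3: rule out other formulas.** None of these matches the printed range of 18.0 to 40.5:

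- z with n = 20: 17.5 to 39.4
- t with n = 20: 18.7 to 42.1
- t with n = 19: 19.3 to 43.4
- one-sided 1.645 with n = 19: 15.1 to 34.0

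**Step 4: size of the gap.** 2.1009/1.960 = 1.072, so the t half-width is 7.2% wider in every row. Equivalently, the printed one is 1 − 1/1.072 = 6.7% narrower.

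**Step 5: coverage if 1.96 were used with the sample SD.** P(|T| < 1.96) on 18 df = 0.934, assuming normal data.

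**Step 6: number of subjects that would give the printed widths with t.**

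- n = 21: t(0.975, 20) = 2.086, and 2.086 × 40/√21 = 18.2, just over 18.0.
- n = 22: t(0.975, 21) = 2.080, and 2.080 × 40/√22 = 17.7.

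So about 22 evaluable subjects per arm would be needed. This only measures the gap and is not a recommendation.

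A minor point: the upper figure of 41 in the text comes from rounding twice, 40.47 to 40.5 and then to 41.

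**The case against.** The strongest reply is that Table 4 conditions on an assumed SD. Given that SD, z × SD/√n is computed correctly, and a normal approximation is a common planning shortcut. That describes how the table was made, but it does not rescue the statement. Both documents say without qualification that 19 subjects will give a 95% interval of this width, to one decimal, and neither calls it approximate. At 18 df the approximation shows in every row and always flatters the design.

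Other points on that side:

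- **The coverage loss is hypothetical.** This stands. The 93.4% applies only if the analysis uses 1.96, which the SAP does not say. It also assumes normality, whereas every mean in Protocol Table 1 exceeds its median, which suggests skew.
- **An estimated SD makes the half-width random.** Also true. Its expectation uses E[s] = 0.986 × SD and runs from 19.0 to 42.8. That still rounds to 19 to 43, and t × SD/√n is the usual figure at an assumed SD.
- **Nothing depends on the difference.** This stands as a statement of consequence: there is no test, target width or decision rule.
- **The SD range is the larger problem.** This stands as a separate matter. Table 1 gives simulated Japanese SDs of 129 to 286 ng/mL for Cmax and 1305 to 2929 ng*hr/mL for AUC. With t and n = 19 these imply half-widths of about 62 to 138 ng/mL and 629 to 1412 ng*hr/mL. The multiplier is wrong for any SD, so a new SD range would not by itself remove the error.

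**Conclusion.** The concern holds. The stated half-widths of 18 to 41 are those of a known-SD interval. With the SD estimated from 19 subjects per arm, the two-sided 95% half-widths at the same assumed SDs are 19 to 43. The quantile is inferred, since the documents do not state it, but the match in all six rows leaves little doubt. The result rests on the plan's own SDs, on 19 evaluable subjects, and on the interval being for an arithmetic mean under approximate normality.

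This is an error in a stated precision figure that appears in two documents. It is not a design failure: the shift is 1.3 to 2.9 units, inside an SD range that itself spans 90/40 = 2.25-fold.

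**What to change.** In Protocol 10.2 (text and Table 4) and SAP 3.2:

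- Replace the six half-widths with 19.3, 24.1, 28.9, 33.7, 38.6 and 43.4.
- Replace the range in the text with 19 to 43, and state that it uses the t distribution on 18 degrees of freedom.
- Leave enrolment at 20 per arm.

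If the SD range is reconciled with Protocol Table 1 at the same time, compute the new table with t; the six values above would then be superseded.

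The cost is a text and table correction. It does not affect conduct, and its only price is a slightly less favourable precision statement.
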